## **7. PLANNED ANALYSIS**

In general the display format of the analysis results will follow BI guideline (7, 8) as much as possible.

This is an open label, uncontrolled, exploratory phase II trial with two patient cohorts. The purpose of this trial is to assess the anti-tumour activity and safety of afatinib monotherapy in patients with urothelial tract carcinoma carrying ERBB2 or ERBB3 mutations or ERBB2 amplifications (Cohort A), and EGFR amplification positive tumours (Cohort B), progressing despite previous platinum based chemotherapy, and thereby to improve their prognosis.

Cohort A of the study follows a two stage design where an analysis for futility will be performed at the end of stage 1 based on first 25 treated patients to determine if the stage 2 of cohort A will be carried out. Cohort B of the study will include up to 10 patients with EGFR amplification. Analysis will be conducted in parallel to, and independent of cohort A.

If the trial is continued into Stage 2 for the ERBB2/ERBB3 cohort (cohort A), an analysis will be prepared to document the efficacy results among the first 25 patients. This analysis will be restricted to the first 25 treated patients in cohort A, and will be conducted after no more of these 25 patients are eligible to be assessed for progression at 24-weeks (6 months).

The primary report will be produced after there are no more patients eligible to be assessed for progression at 24-weeks.

A final report will be produced when all patients have discontinued afatinib and none remain to be assessed for progression at 24-weeks. The data for this report may be included in the primary report, if the gap in time between the last 24-week assessment and the final discontinuation is not too long.

If central radiological reviews are performed, differences in PFS6 outcome and response between the central and investigator reviews will be tabulated for each patient and summarized for all patients. If there are differences, the analyses of PFS6 and response might be repeated using the central assessments.

Company standard displays will be used whenever possible.

Tabulations of frequencies for categorical data will include all possible categories and will display the number of observations in a category as well as the percentage. Percentages will be rounded to one decimal place. The category missing will be displayed only if there are actually missing values.

### **7.1 DEMOGRAPHIC AND OTHER BASELINE CHARACTERISTICS**

Only descriptive statistics are planned for this section of the report.

## 7.2 CONCOMITANT DISEASES AND MEDICATION

Descriptive statistics using standard summary tables for all treated patients are planned for this section of the report.

## 7.3 TREATMENT COMPLIANCE

Descriptive statistics using standard summary tables for the treated set of patients are planned for this section of the report. A summary of whether patients took afatinib according to the protocol and whether they missed any doses will be produced for each planned visit. In addition a summary of overall percentage compliance will be produced using visit dates and the total number of doses missed during the study.

## 7.4 PRIMARY ENDPOINT

The primary endpoint of this study is progression free survival rate at 6 months (PFS6), determined as being alive and progression-free at the 24-week assessment.

Patients who are alive and progression-free at the 24-week (168-day) assessment will be considered successes for PFS6. The following rules are required for PFS6 to be considered a success:

- 1) Consider only valid assessments done before starting of any new anticancer therapy. Also do not consider any assessments done after EOT date+ 30 days.
- 2) Patient has at least one valid assessment demonstrating non-progression on or after day 168 with reference to treatment start day.
- 3) Patient who did not meet the second criterion but has at least one valid non-PD assessment on or after day 154 (22 weeks) and has progression documented after day 182 (26 weeks) is considered as success for PFS6.

Examples:

- i) With SD at Day 156 followed by PD at Day 183 will be considered as success for PFS6.
- ii) With SD at Day 146 followed by PD at Day 170 will not be considered as success for PFS6.
- iii) With SD at Day 156 followed by PD at Day 170 will not be considered as success for PFS6.

For Cohort A, at the end of stage 2, final goal is to test  $H_0: PFS6 \leq 40\%$  vs alternative:  $H_a: PFS6 > 40\%$ . **If we observe fewer than 12 PFS6 successes and fewer than 2 objective responses among the first 25 patients in Stage 1, enrollment for Cohort A will be terminated, and the null hypothesis will be accepted.**

At the end of Stage 2, the significance level for testing the null hypothesis will be calculated as the exact binomial probability i.e.  $\text{Prob}(X > s | n, p = 0.40)$ , where 's' is the observed number of patients achieving PFS6 and 'n' is the total number of patients. A Wilson 90% confidence interval will be provided also.

If trial stops at stage 1, for cohort A, PFS6 will be analysed descriptively and no formal statistical testing will be performed.

PFS6 for Cohort B patients will be analysed descriptively when all patients in Cohort B have completed the 24-week tumour assessment.

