12. Safety lab tests to be performed as described in [Section 5.3.3](#), but should not be repeated if previous tests are older than 48 hours
13. Mandatory for female patients of child bearing potential (post menarchal) within 7 days prior to first treatment and at EOT. To ensure early detection of pregnancy, test might be repeated as necessary during the treatment period depending on the local law
14. ECG is required at screening, at C1V2, and V1 of every third course thereafter (i.e. C4V1, C7V1...) and EOT
15. Tumour assessment by Imaging (CT or MRI) should be performed every 8 weeks (+/- 1 week) calculated from the first treatment day to the end of study treatment. If treatment discontinuation is for other reason than disease progression, further tumour assessments should be obtained as follows: every 8 weeks (+/-1 week) until month 6, and every 12 weeks (+/-2 weeks) from 6 months onwards, until documented progression of disease. Baseline CT/MRI must be performed within 28 days before start of study treatment (if an assessment was performed within this timeframe, patient would not need to repeat this test).
16. Blood and urine for biomarker testing will be collected at screening, then every 4th cycle during treatment, and also at End of Treatment. If a patient has not progressed at End of Treatment then samples should continue to be collected at every 4th follow-up visit and also at the last follow-up visit (as described in [Section 5.5](#)).
17. Pharmacogenetics: one optional blood sample, to be obtained only after signing of PGx consent at any treatment visit.
18. New kit(s) of trial drug must be dispensed at visit1 of each course. If needed (e.g. in case a dose adaptation has to be applied during treatment course), new kit(s) of trial drug might be dispensed outside of the planned visit schedule
19. AE/SAE should be reviewed at every treatment visit, at EOT, EOR and thereafter as described in [section 5.3.6](#).
20. Conclusion of patient participation: should be recorded at the last follow-up visit, when PD/Death occurs, consent withdrawal or death
21. All patients will be followed-up for overall survival at 90 days intervals. For patients who progressed on treatment, the observation period for overall survival starts after the EoR. For patients who have not progressed on treatment, this period starts after the last follow-up for progression visit. The End of the Trial will be achieved as described in [Section 8.6](#).

TABLE OF CONTENTS

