5.2 ASSESSMENT OF EFFICACY

Response and progression will be evaluated in this study using Response Evaluation Criteria in Solid Tumours (RECIST) guideline (version 1.1) ([R09-0262](#)). Tumour response will be assessed by investigator review. Images will be stored in case independent radiology review may need to be introduced at stage 2.

It is critical to continue response evaluation until progression if patients withdrew consent from continuation of treatment but agreed to participate in follow-up tumour assessment.

See [Appendix 10.5](#), RECIST 1.1 Criteria for details on lesion measurements and response assessment.

Tumour assessment by Imaging (CT or MRI) should be performed at screening, and then every 8 weeks (+/- 1 week) calculated from the first treatment day to the end of study treatment . If treatment discontinuation is for other reason than disease progression, further tumour assessments should be obtained as follows: every 8 weeks (+/-1week) until month 6, and every 12 weeks (+/-2 week) from 6 months onwards, until documented progression of disease.

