7.2 NULL AND ALTERNATIVE HYPOTHESES

The exploratory null and alternative hypotheses were set up for the primary endpoint PFS6 based on a two-stage design with H_0 : PFS6 \leq 40% and H_a : PFS6 $>$ 40%. PFS6 is defined as patient being alive and without disease progression at the 24-week tumour assessment.

The null hypothesis for key secondary endpoint ORR is H_0 : ORR \leq 5% and H_a : ORR $>$ 5%. A Hochberg multiple adjustment procedure will be used to control the family-wise error rate at 0.05 (one-sided) for testing PFS6 and ORR.

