7.3.1 Primary endpoint analyses

The primary endpoint of the study is PFS rate at 6 months (PFS6). This will be calculated as the proportion of patients who are alive and without disease progression at the 24-week tumour assessment, out of all analysed patients. Patient prematurely discontinued without the 24-week assessment will be considered as not achieving PFS6 regardless of the reason for discontinuation.

For Cohort A, the first stage will include 25 patients treated with Afatinib, as described in [Section 7.4](#). When the criteria for transition into the second stage are met, the study will move on to the full accrual and there will be up to 70 patients treated in Cohort A.

At the end of the second stage, the significance level for testing the null hypothesis H_0 : PFS6 \leq 40% will be calculated as the exact binomial probability i.e. $\text{Prob}(X \geq s | n, p=0.40)$, where 's' is the observed number of patients achieving PFS6 and 'n' is the total number of patients. A Wilson 90% confidence interval will be provided also.

PFS6 for Cohort B patients will be analysed descriptively when all patients in Cohort B have completed the 24-week tumour assessment.

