7.4 INTERIM ANALYSES

PFS6 and confirmed ORR will be evaluated for the first 25 treated patients when the last patient among them completes the 24-week tumor assessment. If 12 or more patients achieve PFS6, or at least 2 have a confirmed response, the study will move on to the full targeted accrual in Stage 2. The primary analysis will be conducted when 70 patients in Cohort A complete the 24-week tumor assessment.

If fewer than 12 patients achieve PFS6 and fewer than 2 patients have a confirmed response, the trial will be stopped for futility. All patients enrolled will be followed until disease progression and a full analysis will be carried out after all patients discontinue the study.

Stages 1 and 2 of the study will be conducted in a seamless fashion with no interruption in enrolment after treating 25 patients. Therefore by the time of the futility assessment, more than 25 patients might have been treated. The sponsor may however suspend recruitment after enrolling the pre-defined 25 patients in Stage 1 in the event of low likelihood to meet the criteria to move from Stage 1 to Stage 2.

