10.5 APPENDIX 5: RECIST 1.1 CRITERIA

The criteria below are based on RECIST 1.1 ([R09-0262](#)).

The preferred method of assessment is a spiral CT scan with IV and oral contrast, unless IV and/or oral contrast are medically contraindicated. CT scans of the chest, abdomen and other areas of known or newly suspected disease must be performed. Scans of the abdomen, pelvis and other areas of the body, but not chest, may be done with MRI instead of CT.

Skin lesions followed as target lesions must be documented by colour digital photography and must include in the image a ruler with millimetre subdivisions and a label that includes the patients ID and date.

Bone scans (using ^{99m}m-technetium polyphosphonate scintigraphy) are recommended at baseline if the patient has any signs and symptoms consistent with bone metastasis or a

history of bone metastasis. Bone metastasis identified at baseline must be documented and assessed according to RECIST 1.1 at the times of the other tumour measurements indicated in the [flow chart](#). During the study bone scans should be repeated as clinically indicated in patients without bone metastasis at Baseline.

For the purposes of this study, patients should be re-evaluated for response at weeks 8, 16, 24 and every 8 weeks thereafter. In the event of a treatment delay, interruption or discontinuation of treatment, tumour assessment should continue to follow the original schedule.

Follow-up tumour assessments must utilize the same CT/MRI/photographic method and acquisition technique (including use or non-use of IV contrast) as were used for screening assessments to ensure comparability. A chest x-ray or skeletal x-ray which clearly demonstrates a new metastatic lesion may be used to document progression in lieu of CT/MRI/bone scan.

These patients will have their response classified according to the definitions stated below.

Measurability of the disease

Measurable lesions

Lesions that can be accurately measured in at least one dimension with longest diameter ≥ 10 mm (by CT scan, MRI, caliper measurement) or ≥ 20 mm (by chest X-ray). Pathological lymph nodes, defined as lymph nodes with a short axis >15 mm are also measurable.

Measurable disease

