## **5. ENDPOINTS**

### **5.1 PRIMARY ENDPOINT**

This is an open label, uncontrolled, exploratory phase II trial with two patient cohorts. The purpose of this trial is to assess the anti-tumour activity and safety of afatinib monotherapy in patients with urothelial tract carcinoma carrying ERBB2 or ERBB3 mutations or ERBB2 amplifications (Cohort A), and EGFR amplification positive tumours (Cohort B), progressing despite previous platinum based chemotherapy, and thereby to improve their prognosis.

Cohort A of the study follows a two stage design where an analysis for futility will be performed at the end of stage 1 to determine if the stage 2 of cohort A will be carried out. Cohort B of the study will include up to 10 patients with EGFR amplification. Analysis will be conducted in parallel to, and independent of cohort A.

The primary endpoint of this study is progression-free survival rate at six months (PFS6), as assessed at the investigative sites, in the ERBB2/ERBB3 cohort (Cohort A). Patients who are alive and progression-free at the 24-week assessment will be considered successes.

RECIST 1.1 (2) will be used to determine all response and progression endpoints.

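### SAP 7.4 discards tumour scans later than 30 days after end of treatment, so some patients who meet the protocol's PFS6 definition are scored as failures, and the change is not declared

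*SAP*

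**What the plan says.** **The endpoint.** Protocol 7.2 states: "PFS6 is defined as patient being alive and without disease progression at the 24-week tumour assessment". SAP 5.1 agrees: "Patients who are alive and progression-free at the 24-week assessment will be considered successes". Neither makes success depend on still taking afatinib. For early stoppers, Protocol 7.3.1 adds: "Patient prematurely discontinued without the 24-week assessment will be considered as not achieving PFS6 regardless of the reason for discontinuation".

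**The scans.** When treatment stops for a reason other than progression, Flow Chart note 15 says "further tumour assessments should be obtained as follows: every 8 weeks (+/-1 week) until month 6", and Protocol 5.2 repeats this. Appendix 10.5, which names weeks 8, 16 and 24, says: "In the event of a treatment delay, interruption or discontinuation of treatment, tumour assessment should continue to follow the original schedule".

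**The scoring rules.** SAP 7.4 opens with the same definition and then sets three rules.
- Rule 1 ignores scans after new anticancer therapy, and then adds: "Also do not consider any assessments done after EOT date+ 30 days".
- Rule 2 needs a valid non-progression scan on or after Day 168.
- Rule 3 is a fallback. It needs a valid non-progression scan on or after Day 154 and progression documented after Day 182.

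**Declared changes.** SAP section 4 lists only the amended futility criterion.

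**The concern.** The last clause of rule 1 adds a condition that the endpoint definition does not contain. In effect it tests being progression-free at week 24 and either on treatment or within 30 days of EOT. The null of 40% and the alternative of 60% were set for the protocol definition, not for this stricter one.

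No reason is given for the cut. A 30-day span is the length of the residual effect period in SAP 6.1, but there the SAP uses that period to decide which data enter the safety analyses. The sensitivity censoring rules for PFS in SAP Table 7.5.2: 1 contain no such limit, so the same scan could count as progression-free for PFS and be ignored for PFS6.

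At stake are a PFS6 estimate biased downwards and a loss of power on the primary endpoint.

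**Working it through.** **1. Who is affected.** The last scan day that counts is EOT day + 30.
- Scan on Day 168: it counts only if EOT is on or after Day 168 − 30 = Day 138.
- Scan on Day 175 (late edge of the ±1 week window): EOT must be on or after Day 175 − 30 = Day 145.

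Example: EOT on Day 90, no new therapy, stable disease on Day 168. The last counted day is 90 + 30 = Day 120.

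| Text | Result for this patient |
|---|---|
| Protocol 7.2, 7.3.1; SAP 5.1 | Success: alive and progression-free at the 24-week scan |
| Protocol 7.3.1, sentence on early stoppers | Does not apply: the 24-week scan exists |
| SAP 7.4 rules 1 and 2 | Failure: the Day 168 scan is discarded |
| SAP 7.4 rule 3 | No rescue: no counted scan on or after Day 154 |

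**2. The plan's own figures.** Inputs from Protocol 7.7: N=70, null 40%, alternative 60%, Stage 1 of 25 patients. At one-sided 0.025 the critical count is 37, since P(X≥37 | 70, 0.40) = 0.0199. At 0.05 it is 36 (0.0347).
- Ungated power: P(X≥37 | 70, 0.60) = 90.9%, as in Table 7.7: 1.
- With a PFS6-only gate: Σ over x≥12 of Bin(x; 25, p) × P(Y≥37−x | 45, p) = 86.3%, as in the same table.
- P(X≥12 | 25, 0.60) = 92.2%, against 92% in the text.

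**3. Size of the loss.** The documents do not say how many patients are affected. Assume a share of all treated patients is moved from success to failure, so the scored rate p is 60% minus that share.

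| Power for PFS6 | None (p=0.60) | 2% (0.58) | 5% (0.55) | 10% (0.50) |
|---|---|---|---|---|
| Ungated, alpha 0.025 | 90.9% | 84.0% | 68.6% | 36.0% |
| PFS6-only gate, alpha 0.025 | 86.3% | 78.5% | 62.7% | 31.9% |
| Actual Stage 1 rule, alpha 0.025, endpoints independent | 90.5% | 83.5% | 68.0% | 35.6% |
| Actual Stage 1 rule, alpha 0.025, every responder a PFS6 success | 89.9% | 82.8% | 67.5% | 35.4% |
| Hochberg, ungated, endpoints independent | 93.7% | 88.3% | 75.3% | 43.8% |
| Hochberg, actual Stage 1 rule, endpoints independent | 93.3% | 87.7% | 74.6% | 43.3% |

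The rows for the actual Stage 1 rule and for Hochberg take ORR as 15%, the protocol's alternative. For the actual rule at 0.025, power is ungated power minus P(fewer than 12 successes and fewer than 2 responses in Stage 1, total ≥37). Ungated Hochberg power is P(ORR≥8/70) × P(X≥36) + [1 − P(ORR≥8/70)] × P(X≥37), with P(ORR≥8/70) = 84.3%. At p=0.60 this is 0.843 × 0.9426 + 0.157 × 0.9094 = 0.937.

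Two affected patients in 70 (p = 0.60 − 2/70 = 0.5714) give ungated power of 80.1% at 0.025, or 85.2% under Hochberg.

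**4. Futility.** The stopping rule has two parts: "If fewer than 12 patients achieve PFS6 and fewer than 2 patients have a confirmed response, the trial will be stopped for futility". P(X≥12 | 25) falls from 92% to 89%, 82% or 66%. The response criterion still carries most such trials forward, because P(R<2 | 25, 0.15) = 9.3% caps the chance of stopping. That chance rises from 0.7% to 1.0%, 1.7% or 3.2% with independent endpoints. It rises from 1.8% to 2.5%, 3.6% or 5.8% if every responder is a PFS6 success.

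**5. Direction.** If true PFS6 is 40% and 2 points are lost, P(X≥37 | 70, 0.38) = 0.8%, against 2.0% without the loss. The rule is conservative.

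**The case against.** - **A fixed alpha of 0.025 overstates the loss.** This is correct for the design ORR. PFS6 is tested at 0.05 whenever ORR is also significant at 0.05, so the Hochberg rows describe the planned procedure better. They still show a clear loss.
- **The larger shares are unsupported.** An affected patient must stop early without progression, start nothing else, and still be progression-free at week 24. Protocol 1.1 cites median PFS of 2.9 to 4.0 months, and the dose-reduction scheme is meant to keep patients on drug. Ten percent of treated patients is 7 of 70, or one in six of the 42 expected successes (0.60 × 70). This stands: the table shows sensitivity, not a forecast. The firm statement is that each affected patient costs one success.
- **The new-therapy cut is also absent from the definition and undeclared.** True, but it has support elsewhere. Appendix 10.5 ends best-response assessment at further anticancer treatment, and PFS sensitivity rule 4 censors there. The EOT+30 cut has no comparable support.
- **Declaring and justifying the cut, with a protocol-definition sensitivity analysis, would also do.** That would cure the silence, but the primary test would still use an endpoint for which the 40% and 60% were not set.
- **The date is loosely defined.** SAP 7.4 does not say whether EOT means the last dose or the EOT visit, which may be up to 7 days later. If it means the visit, the cut reaches up to 37 days after the last dose. The conflict remains.
- **The consequence is limited.** The trial is exploratory, the rule is conservative, and the scans will exist, so the other count can be recovered. This bears on severity, not on whether the texts agree.

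**Conclusion.** The concern holds. Rule 1 of SAP 7.4 contradicts Protocol 7.2 and 7.3.1, SAP 5.1 and the opening of SAP 7.4 itself. It discards scans that the protocol requires, and SAP section 4 does not mention it. It affects only patients whose EOT is more than 30 days before the week-24 scan and who have neither progressed nor started new therapy.

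The bias runs one way, towards a lower PFS6 estimate and lower power. Type I error is not inflated, and at ORR 15% the chance of a futility stop changes little. The power losses rest on assumed shares of affected patients, a true PFS6 of 60% and, where stated, ORR 15% with the stated link between endpoints. At the smallest share shown, 2% of treated patients, the loss is 6.9 points ungated at 0.025 (90.9 − 84.0) and 5.4 points under ungated Hochberg (93.7 − 88.3). It should be corrected before the primary analysis; it does not undermine the design.

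**What to change.** In SAP 7.4 rule 1, delete the sentence on assessments after EOT + 30 days for the primary PFS6 analysis, and keep the restriction to scans before new anticancer therapy. Report the EOT+30 version as a labelled sensitivity analysis, state whether EOT means last dose or visit date, and give the number of patients whose PFS6 status differs between the two versions.

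The cost is a change of SAP wording and one program filter. No new data are needed, because the protocol already requires the scans. The small downside is that some counted successes will be on scans more than 30 days after EOT; the sensitivity analysis will show how many.

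### SAP 7.4 scores an on-time, progression-free week-24 scan taken before Day 168 as a PFS6 failure when no later valid scan or PD after Day 182 follows; the protocol makes that patient a success

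*SAP*

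**What the plan says.** **Protocol.** Section 7.3.1 defines PFS6 as the "proportion of patients who are alive and without disease progression at the 24-week tumour assessment, out of all analysed patients". It sets no earliest study day. Its only automatic failure is a patient who stops early and has no 24-week assessment. Section 5.2 schedules imaging "every 8 weeks (+/- 1 week) calculated from the first treatment day to the end of study treatment". If treatment stops for a reason other than progression, imaging stays 8-weekly until month 6 and is then "every 12 weeks (+/-2 week) from 6 months onwards, until documented progression of disease". Appendix 10.5 says "patients should be re-evaluated for response at weeks 8, 16, 24 and every 8 weeks thereafter", and keeps the original schedule after discontinuation.

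**SAP.** Section 5.1 and the opening of 7.4 repeat the protocol definition. Section 7.4 then adds three rules:

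- Rule 1 drops scans made after new anticancer therapy starts, and adds: "Also do not consider any assessments done after EOT date+ 30 days".
- Rule 2: "Patient has at least one valid assessment demonstrating non-progression on or after day 168 with reference to treatment start day".
- Rule 3 rescues a patient who misses rule 2 but "has at least one valid non-PD assessment on or after day 154 (22 weeks) and has progression documented after day 182 (26 weeks").

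Of the three worked examples, the third is: "With SD at Day 156 followed by PD at Day 170 will not be considered as success for PFS6". SAP section 4 lists one change to the planned analysis, the futility criterion. It does not mention a Day 168 floor.

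**The concern.** With a window of one week either side, an on-time week-24 scan can fall on Day 161–167. If it shows no progression, the patient meets the protocol definition. Rule 2 rejects the scan because it precedes Day 168. Rule 3 accepts it only if PD is documented later, after Day 182. No rule covers a patient who has neither.

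The outcome is perverse. For the same week-24 scan, documented progression after Day 182 makes the patient a success, while no further record makes the patient a failure. What is at stake is the primary endpoint: observed PFS6 is pushed down relative to the protocol definition, with some loss of power at the final test and at the 12-of-25 limb of the Stage 1 rule.

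**Working it through.** **1. Scoring one scan.** Applied literally, the rules return the SAP's own answers for examples i (success), ii (failure) and iii (failure). Now take a patient with non-PD on Day 163:

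| What follows | Protocol 7.3.1 | SAP 7.4 |
|---|---|---|
| On treatment, non-PD Day 224 | success | success (rule 2) |
| On treatment, PD Day 190 or Day 224 | success | success (rule 3) |
| No further valid scan | success | **failure** |
| Last dose Day 150, next scheduled scan with any result | success | **failure** (rule 1 drops it) |
| Death Day 190 without imaged PD | success | **failure** |
| New therapy Day 180, scan Day 224 | success | **failure** (rule 1 drops it) |

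A single non-PD scan on Day 168 is a success under both.

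**2. Why the Day 150 case cannot be rescued.**

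- The EOT visit, which includes imaging, is within 7 days of the last dose: by Day 157, before Day 168.
- Rule 1 limit: 150 + 30 = Day 180, or 157 + 30 = Day 187 if the EOT date means the visit.
- Next scheduled scan at the earliest: week 32, 224 − 7 = Day 217 (Appendix 10.5), or week 36, 252 − 14 = Day 238 (section 5.2). Both are beyond Day 187.

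**3. Day count.** SAP 7.4 equates week 24 with 168 days. SAP 6.7 calls the first dose Day 1, so 24 elapsed weeks end on Day 169. The on-time days before the floor are 161–167 on the first count and 162–167 on the second.

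**4. Reproducing the protocol's power.** Inputs from protocol 7.2, 7.4 and 7.7: N = 70, null 40%, alternative 60%, one-sided alpha 0.025 or 0.05, Stage 1 limb of at least 12 of 25. I use the protocol's tail, P(X ≥ s); the SAP prints X > s, which is a separate matter.

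- Critical values: 37 of 70 (p = 0.0199) and 36 of 70 (p = 0.0347).
- Power: P(X ≥ 37 | 70, 0.6) = 90.9% and P(X ≥ 36 | 70, 0.6) = 94.3%.
- Requiring at least 12 of 25 at Stage 1: 86.3% and 88.8%. All four match Table 7.7:1.
- P(X ≥ 12 | 25, 0.6) = 92.2%, against 92% in the protocol.

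**5. Effect of a loss.** Suppose a share r of true successes is rescored as failures, so the observable rate is 0.6(1 − r). The values of r are assumptions. False stopping = P(X < 12 | 25) × P(at most 1 response of 25). At ORR 15% the second factor is 1 − 0.9069 = 0.0931, taking response as independent of PFS6.

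| r | Expected lost (70 × 0.6 × r) | Power 0.025, unadjusted / with Stage 1 | Power 0.05, unadjusted / with Stage 1 | P(≥12 of 25) | False stop, ORR 15% |
|---|---|---|---|---|---|
| 0 | 0 | 90.9 / 86.3% | 94.3 / 88.8% | 92.2% | 0.7% |
| 1% | 0.4 | 89.1 / 84.2% | 93.0 / 87.1% | 91.3% | 0.8% |
| 2% | 0.8 | 87.1 / 81.9% | 91.5 / 85.2% | 90.2% | 0.9% |
| 5% | 2.1 | 79.5 / 73.7% | 85.6 / 78.3% | 86.6% | 1.2% |

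At ORR 5% the second factor is 0.6424, and false stopping runs from 5.0% (r = 0) to 8.6% (r = 5%). Under the null, r = 2% lowers the chance of 37 or more of 70 from 0.0199 to 0.0141.

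A single patient can decide the result near the boundary: 36 of 70 gives p = 0.035 and 35 of 70 gives p = 0.057.

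**The case against.** **The floor may be deliberate.** SAP 7.4 openly ties week 24 to 168 days. A SAP may make the protocol more precise, and a strict floor is a defensible conservative choice in an open-label, investigator-assessed, single-arm trial. That stands as a possible intention. However, nothing declares it, and the scans in the three examples that precede PD fall on Days 146 and 156, outside the protocol window. None of them settles an on-time scan.

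**PD on Day 168–182.** A reader might infer that SD on Day 163 followed by PD on Day 175 is also wrongly scored. The documents do not support that. Example iii fails a patient whose PD follows shortly after Day 168. SAP 6.7 says the last image in an interval is used so that progression is not missed. Protocol 5.1.1 asks for no progression by the 24-week assessment, whose window runs to about Day 175. Such patients look like intended failures and are not part of this point.

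**SAP 6.7 and code E1 prove little.** The ±4-week slot and the Day 140 violation limit do place a Day 163 scan at week 24, but they would equally admit Day 146. Nor does 6.7 clearly govern PFS6: in example i, Days 156 and 183 share the week-24 slot, yet the earlier SD prevails.

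**The Day 150 case needs a scan between visits.** EOT imaging is due by Day 157 and the EoR visit no earlier than Day 180, with no imaging planned at EoR. This narrows the exposure. The case remains possible, because protocol 5.2 and Appendix 10.5 keep the 8-week schedule after treatment stops.

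**Few patients may be affected.** Patients treated past Day 168 generally get a week-32 or EOT scan that settles the matter. No document supports 1%, 2% or 5%.

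**Conclusion.** The gap is real and lies in the scoring of the primary endpoint. An on-time non-PD scan before Day 168, with no valid scan from Day 168 and no PD documented after Day 182, is a success under protocol 7.3.1 and a failure under SAP 7.4, and SAP section 4 does not declare the difference. The permanent cases are:

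- (a) treatment stopped before week 24, with an on-time non-PD scan within EOT + 30 days, where rule 1 discards the next scheduled scan;
- (b) death after week 24, or new anticancer therapy, before another valid scan.

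It would be wrong to read this as all early scans failing: a later valid non-PD scan, or valid PD after Day 182, rescues the patient. It would also be wrong to build a large Stage 1 loss on scans still pending at the data cut. The documents do not say how a pending scan is scored, and the share of early scans is unknown.

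The effect is conservative for type I error. The power losses tabulated above rest entirely on assumed shares. At ORR 15% the response limb keeps false stopping at Stage 1 to 1.2% or less, against 0.7% with no loss. The rule should be corrected or declared before analysis, but it does not undermine the design.

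**What to change.** Add to SAP 7.4: a valid non-PD assessment inside the protocol week-24 window but before Day 168 counts as a success if the patient is alive at the nominal week-24 day and no PD is documented on or before Day 182. Keep rules 1 to 3 otherwise. Examples i–iii keep their results, because Days 146 and 156 lie outside the window. SD on Day 161 then PD on Day 169 remains a failure.

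Also use one day count in SAP 6.7 and 7.4 (window start and nominal day 161/168 or 162/169), and state whether the SAP 6.7 last-assessment rule applies to PFS6.

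If the Day 168 floor is deliberate, list it in SAP section 4 as a change from the protocol. Then report PFS6 under the protocol-window rule as a sensitivity analysis, both at Stage 1 and at the primary analysis.

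The cost is SAP wording and derivation code, with no new data. The downside is that status may be read up to 7 days before week 24, as protocol 5.2 already permits. One oddity stays: under rule 2, SD on Day 168 then PD on Day 169 succeeds, while SD on Day 167 then PD on Day 182 fails.
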